Sample size assessment - The standard deviation used for the sample size calculations was calculated from the observed value of distal antral activity in healthy volunteers in the absence of any treatment: 14.3 ± 0.66 (SD) (10,13). Comparison of 8 Participants in the active vs. sham treatment arms will have sufficient power to detect a difference between the 2 groups (Unpaired t-test; Parallel group design) of distal antral MI of 0.995 units or 7.0% relative to controls (10,13). It is to be noted that the antral MI measurement is on a logarithmic scale and, therefore, a 10% reduction in **antral** motility index is clinically relevant since it is associated with reduction in gastric emptying rate.

Response	Mean	SD	Predicted detectable effect size (%(absolute #)), n=8 per group unpaired analysis
Postprandial distal antral motility index	14.3	0.66	7.0% (0.995 MI units)

Data obtained from ref. 10; predicted detectable effect size is shown with 80% power, $\alpha=0.05$.

Statistical Methods

It is anticipated that the primary endpoint (the logarithmically transformed antral MI) will be normally distributed. We shall use an unpaired student's t-test to compare the antral MI in the sham versus active treatment groups.

An interim analysis will be performed for **“futility” assessment** after the first 8 participants. In such an analysis, we would have 4 patients per group, assessed in unpaired t test based on parallel group design. Using the same SD of 0.66, a comparison of 4 patients per group would have sufficient power to detect a significant difference in antral motility index of 1.572 (11 %). If the interim analysis shows that the antral MI difference between the 2 groups is <0.75 ($\sim 5\%$), we would consider whether it would be futile to continue the study and completing 16 participants. On the other hand, if the difference in mean antral MI is >0.75 in the two groups, we would complete the study. Since this interim analysis is conducted for “futility” rather than for efficacy, we will **not** correct the α statistic from 0.05 (e.g. to 0.025) on completion of the pre-specified sample of 16 subjects.

Anticipated Results and Significance

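### The interim futility bar of 0.75 MI units is above the 0.708 that the final test needs at the planning SD, so it is set too high near its edge

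*Combined protocol and SAP*

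**What the plan says.** All of this is in the Statistical Analysis part of the combined protocol and SAP.

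- **Sample size assessment.** The SD is 0.66 on a mean of 14.3. With 8 per group, an unpaired t-test, 80% power and α = 0.05, the detectable difference is 0.995 MI units (7.0%). A 10% reduction in the antral "motility index is clinically relevant since it is associated with reduction in gastric emptying rate"; on a mean of 14.3 that is 1.43 units.
- **Statistical Methods, interim analysis.** After 8 participants, "a comparison of 4 patients per group would have sufficient power to detect a significant difference in antral motility index of 1.572" (11%). The rule has two sides. "If the interim analysis shows that the antral MI difference between the 2 groups is <0.75" (about 5%), then "we would consider whether it would be futile to continue the study and completing 16 participants". Otherwise, "if the difference in mean antral MI is >0.75 in the two groups, we would complete the study".
- **Final α.** Because the look is for futility only, the plan will not "correct the α statistic from 0.05 (e.g. to 0.025) on completion of the pre-specified sample of 16 subjects".

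The plan gives no basis for 0.75. It does not state the smallest difference that would be significant at the end, or how often a trial with a real effect would fall below the bar.

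**The concern.** A futility bar should pick out interim results from which success is unlikely. It can therefore sit well below the difference that the completed trial needs, because half of the data are still to come. Here it sits slightly above that difference. At the planning SD, an interim difference between 0.708 and 0.75 is on the futility side at 4 per group, yet the same difference at 8 per group would give p < 0.05.

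At stake is the chance of giving up a trial that would have succeeded. The stated 80% power takes no account of the interim look. The only number offered to guide the decision is 0.75.

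**Working it through.** **Inputs.** SD 0.66, mean 14.3, 8 per group at the end, 4 per group at the interim, α = 0.05, unpaired t-test, detectable difference 0.995, relevant reduction 10% = 1.43, bar 0.75. All are from Statistical Analysis. Sidedness is not stated.

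**1. Reproduce the plan's figures.** Two-sided noncentral-t power at SD 0.66 gives detectable differences of 0.994 with 8 per group (plan: 0.995) and 1.571 with 4 per group (plan: 1.572). One-sided tests would give 0.863 and 1.317. The plan's figures therefore imply a two-sided test.

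**2. Smallest significant difference at the end.**
SE = 0.66 × √(2/8) = 0.33; t(14, 0.975) = 2.145; 2.145 × 0.33 = **0.708** (5.0% of 14.3). The bar is 0.75 (5.2% of 14.3).

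**3. Chance of falling below 0.75 at the interim.**
SE = 0.66 × √(2/4) = 0.467, and the chance is Φ((0.75 − true effect)/0.467).
- True 0.995: Φ(−0.525) = 30%.
- True 1.43: Φ(−1.457) = 7%.
- True 0: Φ(1.607) = 95%. If the rule is read on the absolute difference, this becomes 89%.

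**4. What the flagged trials would have shown.** Two-stage trials were simulated with normal data, SD 0.66 and a final t-test on the estimated variance.

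| True reduction | Below 0.75 | Power, no stopping | Power if every flag stops | Flagged trials significant if completed |
|---|---|---|---|---|
| 0.995 | 30% | 80% | 64% | 55% |
| 1.43 | 7% | 98% | 92% | 85% |

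Check on the first row: (80.0 − 63.6)/30.0 = 55%.

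**5. Conditional power by interim result** (same simulation).
- Interim 0.74: about 60% on the current trend, 77% if the true effect is 0.995, 94% if it is 1.43.
- Current trend, further down: 47% at 0.65, 26% at 0.50, no more than 7% at 0.29. It passes 50% at about 0.67.

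**6. A bar tied to the plan's own 10% effect.**
The 95% half-width at 4 per group is 2.447 × 0.467 = 1.14, and 1.43 − 1.14 = **0.29**. Below 0.29, the interval at the planning SD excludes a 10% reduction. The table shows two versions: a fixed 0.29, and an upper 95% limit that uses the observed pooled SD.

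| Rule | Flagged at 0.995 | Power at 0.995 if every flag stops | Flagged at 1.43 | Flagged at 0 |
|---|---|---|---|---|
| 0.75 (plan) | 30% | 64% | 7% | 95% |
| Fixed 0.29 | 6.5% | 79% | 0.7% | 73% |
| Upper limit, observed SD | 12% | 73.5% | 2.5% | 72.5% |

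The observed-SD version does worse because, with 6 degrees of freedom, a chance low SD can flag a trial at reductions above 0.29. At 0.995, 54% of the trials it flags would still have been significant, no better than the present rule. For the fixed bar that share is (80.0 − 78.6)/6.5 ≈ 22%.

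**The case against.** Several points stand and limit the finding.

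- **The rule does not stop the trial.** A reader might infer that a result under 0.75 is declared futile. The text commits the team only on the upper side; below the bar they would consider the matter. The 64% is therefore a worst case. The interim is also to be assessed by t-test, so the observed SD and interval would be available to that discussion.
- **Most of the flagged region is not promising.** A reader might infer that results below the bar are generally more likely than not to succeed. On the current trend this holds only between about 0.67 and 0.75. The 55% and 85% assume that the true effect is already 0.995 or 1.43. With zero effect, only 1.5% of flagged trials would go on to a significant reduction.
- **The overlap is narrow and depends on the SD.** The band from 0.708 to 0.75 holds about 3% of interims at a true 0.995. It disappears once the SD reaches about 0.70 (0.75 × 2/2.145). The critical difference is 0.536 at SD 0.5 and 0.858 at SD 0.8. Still, 0.66 is the SD that the plan uses for both its calculations.
- **No claim of no effect is made.** A reader might infer that an early stop would be reported as absence of effect. The plan speaks only of whether to continue.
- **A high bar can be a choice.** The study involves tube placement and fluoroscopy, 0.75 is about half of the relevant 1.43, and only 7% of trials with that effect are flagged. Giving up power for a 95% flag rate under no effect could be defended. The plan does not make that argument or show the price.

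**Conclusion.** The concern holds in a limited form. On the plan's own SD and test, the futility bar (0.75) exceeds the difference needed for significance at the end (0.708). The narrow overlap is the symptom. The larger cost is that 30% of trials with the effect the study is sized for are flagged, and 55% of those would have been significant. Power lies between 80% (no flag acted on) and about 64% (every flag acted on), and the plan states only the 80%.

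This rests on SD 0.66, normal data, a two-sided final test and the difference read as sham minus active. A larger SD reverses the ordering of the two thresholds. A one-sided final test, with a critical difference of 0.581, would strengthen the point. The documents do not support saying that the bar is wrong throughout its range or that the trial would be stopped automatically. This is a cheap improvement rather than a flaw that undermines the trial.

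**What to change.** In Statistical Methods, in both sentences of the interim rule, replace 0.75 (~5%) with a fixed bar of about 0.29 MI units on the signed reduction, sham minus active. State that it is 1.43 − 1.14, computed with the planning SD and not with the observed pooled SD.

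Add its properties: 6.5% flagged and about 79% power at a true 0.995 if every flag leads to a stop; 0.7% flagged at 1.43; 73% flagged at zero effect. Say that after any early stop the difference will be reported with its 95% interval.

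**Cost.** Two edited sentences and one or two added. Under no effect, the chance of a futility flag falls from 95% to 73%. If every flag stops the trial, the average enrolment rises from 16 − 8 × 0.946 = 8.4 to 16 − 8 × 0.731 = 10.2, or about 2 participants. The maximum of 16 and the final α do not change.
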